7. ANALYSIS INTERPRETATION

Except for analysis on objectives with predefined success criterion and an appropriate type I error control (i.e. confirmatory analyses), no comparative analyses will be performed.

With respect to confirmatory analyses the interpretation must be done in a hierarchical manner.

Each objective can only be reached if the associated criteria is met and all previous objectives have been reached (see Figure 1).

Figure 1 Sequence for evaluating the study objectives

The sequence of testing for anti-poliovirus antibodies was based on the fact that polio type 2 is eradicated and serotype 1 is the most prevalent followed by type 3 as per a 10:1 ratio (cases confirmed worldwide in the calendar year 2012 [data in World Health Organization (WHO) headquarter as of 12 March 2013]).

8. CONDUCT OF ANALYSES

8.1. Sequence of analyses

The final data analysis will include all data up to one month after the third dose of DPT-IPV vaccine. These analyses will include the final analysis of immunogenicity and the final analysis of solicited and unsolicited symptoms and SAEs from the first dose up to Visit 7.

| Description | Analysis ID | Disclosure Purpose (CTRS=web posting, SR=study report, internal) | Dry run review needed (Y/N) | Study Headline Summary (SHS) requiring expedited communication to upper management (Yes/No) | Reference for TFL |
|----------------|-------------|--|--|---|---------------------------------------|
| Final analysis | E1_01 | Study Report CTRS | Y for in-text tables, to be generated between LSLV and 1 month before Data Base Freeze | Yes | All tables from TFL dated 12-SEP-2016 |

8.2. Statistical considerations for interim analyses

All analyses will be conducted on final data and therefore no statistical adjustment for interim analyses is required.

9. CHANGES FROM PLANNED ANALYSES

It was planned in the protocol to exclude subjects without any available results for both sampling time points (Visits 4/5 and 7) from the ATP cohort for analysis of immunogenicity. Actually, subjects without any available results for the sampling time point at Visit 7 will be excluded from the ATP cohort for analysis of immunogenicity.

10. SPECIFICATIONS FOR TABLES, LISTINGS AND FIGURES

The TFL TOC provides the list of tables/listings and figures needed for the study report. It also identifies the tables eligible for each analyses and their role (synopsis, in-text, post-text, SHS,...).

The following group names will be used in the TFLs:

| Group order in tables | Group label in tables | Group definition for footnote |
|-----------------------|-----------------------|---|
| 1 | Co-Administered | DPT-IPV vaccine administered according to a 3, 4, 6 month schedule and the liquid HRV vaccine according to a 2, 3 month schedule |
| 2 | Staggered | DPT-IPV vaccine administered according to a 3, 4, 5, 6 month schedule and the liquid HRV vaccine according to a 2, 3, 5 month schedule. |

11. ANNEX 1 STANDARD DATA DERIVATION RULE AND STATISTICAL METHODS

11.1. Statistical method references

The exact two-sided 95% CIs for a proportion within a group will be the Clopper-Pearson exact CI [Clopper CJ, Pearson ES. The use of confidence or fiducial limits illustrated in the case of binomial. *Biometrika*. 1934;26:404-413].

The standardised asymptotic two-sided 95% CI for the group difference in proportions is based on the method described in the following paper: Robert G. Newcombe, interval estimation for the difference between independent proportions: comparison of eleven methods, *Statist Med*. 1998; 17, 873-890. The standardised asymptotic method used is the method six.

11.2. Standard data derivation

11.2.1. Date derivation

- SAS date derived from a character date: in case day is missing, 15 is used. In case day & month are missing, 30June is used.
- Onset day for an event (ae, medication, vaccination, ...): the onset day is the number of days between the last study vaccination & the onset/start date of the event. This is 0 for an event starting on the same day as a vaccination. See SAS date derived in case the start date of the event is incomplete.

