6.4. Analysis of safety

6.4.1. Analysis of safety planned in the protocol

The safety analysis will be based on the TVC.

The incidence by dose, overall per dose and overall per subject, with its exact 95% CI of

- any adverse event (solicited or unsolicited, local or general),
- at least one local adverse event (solicited or unsolicited), and,
- at least one general adverse event (solicited or unsolicited),

during the 8-day (Days 0-7) follow-up period will be tabulated. The same calculations will be performed for any Grade 3 (solicited or unsolicited) symptoms, related and for any adverse event requiring medical attention.

For each type of solicited symptom, the incidence during the 8-day (Days 0-7) follow-up period of the symptom (any grade, Grade 3, related, Grade 3 related, requiring medical advice) will be tabulated as follows:

- at each dose, the percentage of doses followed by the reporting of a symptom and its exact 95% CI,
- over all the doses, the percentage of subjects reporting the symptom and its exact 95% CI,
- over all the doses, the percentage of doses followed by the reporting of a symptom and its exact 95% CI,
- for fever, additional analyses will be performed by 0.5°C increments.

The percentage of subjects who receive concomitant medication, who receive antipyretic medication and prophylactic antipyretic medication during the 8-day (Days 0-7) and 31-day (Days 0-30) follow-up period post-vaccination will be tabulated by dose, overall per subject and over all the doses.

The verbatim reports of unsolicited symptoms will be reviewed by a physician and the signs and symptoms will be coded according to MedDRA. Every verbatim term will be matched with the appropriate Preferred Term. The percentage of subjects with unsolicited symptoms occurring during the 31 days (Days 0-30) with its exact 95% CI will be

tabulated by preferred term. Similar tabulation will be done for Grade 3 unsolicited symptoms and for unsolicited symptoms causally related to vaccination.

Subjects who experienced at least one SAE during the entire study period (from the first dose till the end of the study [Visit 7]) will be reported and the SAEs will be described in detail.

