6.4.2. Additional considerations

- In line with the endpoint description separate analysis will be made for solicited symptom, unsolicited AE within 31 days post vaccination and concomitant medication for
 - The 2 HRV doses
 - The first DTPa-IPV dose
- In line with the HRV project standard, the primary analysis of solicited symptom will be performed by administered dose regardless of whether a solicited symptom has been documented as present/absent. A complementary analysis by documented dose in which only dose for which presence/absence of the symptoms is recorded will be performed in case the percentage of documented dose among administered dose exceed 5% for one visit or a group.
- The incidence by dose, overall per dose and overall per subject of any grade 3 adverse event (solicited or unsolicited, local or general) with causal relationship to vaccination during the 8-day (Days 0-7) follow-up period will be tabulated with exact 95% CI.
- The percentage of subjects with unsolicited symptoms requiring medical attention occurring within 31 days (Days 0-30) post-vaccination with its exact 95% CI will be tabulated by group and preferred term. Similar tabulation will also be done for unsolicited AEs rated as grade 3 in intensity with causal relationship to vaccination.
- The percentage of subjects with causally related AEs from the first study vaccine until Visit 7 will be tabulated by group and preferred term.
- Medications will be coded using the GSKDRUG dictionary. Medications which started during the specified periods (Days 0-7 and Days 0-30) will be counted rather than all medications taken during the specified periods.
- For clinicaltrials.gov and EudraCT posting purposes, a summary of subjects with all combined solicited (regardless of their duration) and unsolicited adverse events will be provided. Solicited adverse events will be coded by MedDRA as per the following codes:

| Solicited symptom | Lower level code | Lower level term |
|----------------------------|------------------|---------------------------|
| Pain at injection site | 10022086 | Injection site pain |
| Redness at injection site | 10022098 | Injection site redness |
| Swelling at injection site | 10053425 | Injection site swelling |
| Fever | 10016558 | Fever |
| Irritability/Fussiness | 10057224 | Irritability postvaccinal |

| Solicited symptom | Lower level code | Lower level term |
|-------------------|------------------|------------------|
| Diarrhoea | 10012727 | Diarrhea |

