11.2.2. Dose number

- The study dose number is defined in reference to the number of study visits at which vaccination occurred. More specifically dose 1 refers to all vaccines administered at the first vaccination visit while dose 2 corresponds to all vaccinations administered at the second vaccination visit even if this is the first time a product is administered to the subject.
- Relative dose: the relative dose for an event (AE, medication, vaccination) is the most recent study dose given before an event. In case the event takes place on the day a study dose is given, the related dose will be that of the study dose, even if the event actually took place before vaccination. For instance, if an adverse event begins on the day of the study vaccination but prior to administration of the vaccine, it will be assigned to this dose. In case a study dose is not administered and an event occurs after the subsequent study dose (eg 3rd study dose), the relative dose of the event will be study dose associated to the subsequent study dose (eg dose 3).
- The number of doses for a product is the number of time the product was administered to a subject.
- The incidence per dose is the number of vaccination visits at which an event was reported among all vaccination visits.

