11.2.5. Safety

- For analysis of solicited, unsolicited adverse events (such as serious adverse events or adverse events by primary MedDRA term) and for the analysis of concomitant medications, all vaccinated subjects will be considered. Subjects who did not report the event or the concomitant medication will be considered as subjects without the event or the concomitant medication respectively.

- In case there will be more than 5% of subjects without documented dose for solicited symptoms (i.e., symptom screen not completed), sensitivity analysis will include only vaccinated subjects for doses with documented safety data (i.e., symptom screen completed).
- The following rules will be used for the analysis of solicited symptoms:
 - Subject who didn't document the presence or absence of a solicited symptom after one dose will be considered not having that symptom after that dose in the analysis done on "administered dose"
 - Subjects who documented the absence of a solicited symptom after one dose will be considered not having that symptom after that dose.
 - Subjects who documented the presence of a solicited symptom and fully or partially recorded daily measurement over the solicited period will be included in the summaries at that dose and classified according to their maximum observed daily recording over the solicited period.
 - Subjects who documented the presence of a solicited symptom after one dose without having recorded any daily measurement will be considered as having that symptom after that dose).
- The maximum intensity of local injection site redness/swelling will be coded as follows:

| Grade | Redness/swelling |
|-------|-------------------------|
| 0 | Absent |
| 1 | > 0 mm and \leq 5 mm |
| 2 | > 5 mm and \leq 20 mm |
| 3 | > 20 mm |

- For the analysis, temperatures will be coded as follows for oral, axillary or tympanic route:

| Grade | Temperature |
|-------|-------------------------------|
| 0 | < 37.5°C |
| 1 | \geq 37.5°C - \leq 38.0°C |
| 2 | > 38.0°C - \leq 39.0°C |
| 3 | > 39.0°C |

For rectal route, temperatures will be converted to axillary setting by subtracting 0.5°

- Note that for all tables described in this section, the way the percentage of subjects will be derived will depend on the event analysed (see table below for details). As a result, the N value will differ from one table to another.

| Event | N used for deriving % per subject for Vaccination phase | N used for deriving % per dose for Vaccination phase |

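### Partial start dates of unsolicited AEs and medications are imputed without regard to Dose 1, so some post-vaccination events can be dated before any vaccination and others assigned to the wrong dose

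*SAP*

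**What the plan says.** SAP section 11.2.1 fixes the substitution for partial dates: "in case day is missing, 15 is used. In case day & month are missing, 30June is used". The same section defines onset: "the onset day is the number of days between the last study vaccination & the onset/start date of the event". It then sends incomplete event dates to the substitution rule: "See SAS date derived in case the start date of the event is incomplete". Section 11.2.2 attributes the event: "the relative dose for an event (AE, medication, vaccination) is the most recent study dose given before an event".

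These derived dates decide which events enter the windowed safety tables. Section 6.4.1 says: "The percentage of subjects with unsolicited symptoms occurring during the 31 days (Days 0-30) with its exact 95% CI will be" tabulated by preferred term, and its 8-day incidence tables also include unsolicited events. For medications, section 6.4.2 says: "Medications which started during the specified periods (Days 0-7 and Days 0-30) will be counted". Section 6.4.2 also asks for separate analyses of the two HRV doses and the first DPT-IPV dose, so dose attribution matters.

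Nothing in these sections bounds an imputed date by a vaccination date or says what to do when it falls before Dose 1.

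**The concern.** A fixed 15th of the month ignores information that the record does contain. With Dose 1 on 20 January and an event on 22 January whose day is missing, the imputed date is 15 January, five days before any study vaccine. There is then no last vaccination from which to count and no relative dose to assign. Under section 2, unsolicited symptoms are collected after study doses, so such a date conflicts with how the data arise.

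Section 11.2.2 resolves same-day ambiguity towards the dose, even for an event that began before the injection. The date rule can do the opposite. What is at stake is the completeness of the Days 0-7 and Days 0-30 tables of unsolicited AEs and medications after Dose 1, and the attribution of events to HRV or DPT-IPV at later doses.

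**Working it through.** The SAP states no figure on this point, so there is none to reproduce. The check applies the rule to every possible date.

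**Inputs**
- Imputation, onset and relative-dose rules: sections 11.2.1 and 11.2.2.
- Vaccination days at the optimal intervals of Table 4: Co-administration 0, 30, 60, 116; Staggered 0, 30, 45, 75, 120.
- Assumptions (the SAP gives no enrolment dates): each dose date equally likely over 365 days, and true onset uniform over the window and before the next dose. With doses 30 days apart, Day 30 belongs to the next dose, so the Days 0-30 base is 365 × 30 = 10,950. For Days 0-7 it is 365 × 8 = 2,920.

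**Day missing, imputed before Dose 1.** This needs a dose after the 15th and onset in the same month. In a month of L days there are j = 1, …, L − 15 such dose positions, counted back from month end, each with j remaining days.
- Days 0-30: the sum of j is (L − 15)(L − 14)/2, giving 136, 120 and 91 for L = 31, 30 and 28. Over a year, 7 × 136 + 4 × 120 + 91 = 1,523, and 1,523/10,950 = **13.9%**. For one isolated dose with all 31 days counted, 1,523/11,315 = 13.5%.
- Days 0-7: the sum of min(8, j) is 100, 92 and 76. Over a year, 7 × 100 + 4 × 92 + 76 = 1,144, and 1,144/2,920 = **39.2%**.

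**Day missing, by visit (dose and window both correct)**

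| Visit and true window | Before the dose | Correct |
|---|---|---|
| Next dose 30 days later, Days 0-30 | 13.9% | 74.6% |
| Staggered Visit 2 (next dose 15 days later), Days 0-30 | 27.7% | 49.3% |
| All of these visits, Days 0-7 | 39.2% | 26.3% |

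The rest of the Days 0-30 events move to the next dose: 100 − 13.9 − 74.6 = 11.5%, and 100 − 27.7 − 49.3 = 23.0% at Staggered Visit 2. At visits after the first, an event imputed before its dose goes to the previous dose.

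**Day and month missing.** After Dose 1, 30 June keeps the right dose and the 31-day window only if Dose 1 fell on one of 30 dates: 30 × 30 = 900, and 900/10,950 = 8.2%. For Days 0-7, 8 × 8 = 64, and 64/2,920 = 2.2%. The date falls before Dose 1 in 46.4% (Days 0-30) and 49.5% (Days 0-7). For example, with a dose on 10 September and onset on 12 September, the imputed day is −72.

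**Effect of a bound at Dose 1 (day missing, Dose 1 events).** Events imputed before Dose 1 take its date. Correct placement rises from 74.6% to 74.6 + 13.9 = 88.5% for Days 0-30, and from 26.3% to 26.3 + 39.2 = 65.5% for Days 0-7. Events after later doses are unchanged by this bound.

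**The case against.** A reader might infer that the rule understates safety events after every dose, and that about a quarter of day-missing events are lost (13.5% before the dose plus 11.1% after Day 30 for an isolated dose). The SAP does not support that.
- Those figures count only outflow. Under a uniform event rate, 11.1% of events in the 31 days before a dose and 13.5% of those on Days 31-61 are moved in, so the flows cancel. Dose 1 is the exception, because AEs are collected only from the first study vaccine.
- At later doses an event imputed before its dose is counted from the previous one. Of day-missing events truly on Days 0-30, the share still inside some analysed 31-day window is 86.1% at the first visit, 88.5% at Co-administration Visit 2 and Staggered Visit 3, and 100% at Staggered Visit 2. The 11.5% missing at the second pair go forward to a DPT-IPV dose outside the windowed analyses. That is a possible loss, not a demonstrated net understatement.
- Solicited symptoms are "classified according to their maximum observed daily recording over the solicited period" (section 11.2.5), so the Days 0-7 percentages do not apply to them.
- Safety is descriptive (section 7), the same rule serves both groups, and SAEs and causally related AEs are also reported through Visit 7.

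All of this stands and limits the point. What remains is that events after Dose 1 can be dated before it with no stated handling, and that events after later doses can be attributed to the wrong dose.

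**Conclusion.** The point holds in limited form and is minor. Among unsolicited AEs and medications with the start day missing, about 14% of those truly on Days 0-30 after Dose 1, and 39% of those on Days 0-7, would be dated before Dose 1 and drop out of the post-vaccination tables. At later doses the rule mainly misattributes: about 25% of day-missing Days 0-30 events go to a wrong dose where visits are 30 days apart, and 51% at Staggered Visit 2.

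These are shares of partial-date records, not of all events. They rest on uniform calendar dates, uniform onset and optimal visit spacing; the mechanism does not. The SAP gives no count of partial dates, and nothing in it shows that any will lack the month. The primary immunogenicity endpoint does not use this rule.

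**What to change.** Keep the 15th as the default in section 11.2.1 and add bounds for AE and medication start dates:
1. If the recorded month or year is compatible with onset on or after Dose 1, and the record does not say that it began before vaccination, an imputed date earlier than Dose 1 is replaced by the Dose 1 date.
2. An imputed date may not fall after the visit or date at which the event was reported. Where that visit is also a vaccination visit, state how this cap works with the same-day rule of section 11.2.2, which would otherwise give the event to the new dose.
3. If the month is missing, impute between Dose 1 (or the last visit at which the event was not reported) and the reporting visit, instead of 30 June.

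Do not make the latest dose date in the month the general rule. With visits 15-30 days apart, it lowers correct placement of day-missing Days 0-30 events from 74.6% to 50.9% at most visits, and from 49.3% to 26.3% at Staggered Visit 2. It also moves late events into Days 0-7.

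The cost is a small programming change and a few lines of text. The downside is that a few events or medications that truly began before Dose 1 may be counted as post-vaccination.

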11.2.2. Dose number

- The study dose number is defined in reference to the number of study visits at which vaccination occurred. More specifically dose 1 refers to all vaccines administered at the first vaccination visit while dose 2 corresponds to all vaccinations administered at the second vaccination visit even if this is the first time a product is administered to the subject.
- Relative dose: the relative dose for an event (AE, medication, vaccination) is the most recent study dose given before an event. In case the event takes place on the day a study dose is given, the related dose will be that of the study dose, even if the event actually took place before vaccination. For instance, if an adverse event begins on the day of the study vaccination but prior to administration of the vaccine, it will be assigned to this dose. In case a study dose is not administered and an event occurs after the subsequent study dose (eg 3rd study dose), the relative dose of the event will be study dose associated to the subsequent study dose (eg dose 3).
- The number of doses for a product is the number of time the product was administered to a subject.
- The incidence per dose is the number of vaccination visits at which an event was reported among all vaccination visits.

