- Details of the HRV Immunogenicity sub-cohort are provided in Table 3. The sub-cohort will consist of 146 subjects (the first 73 subjects enrolled into the study from each study group).

Table 3 Sub-cohorts

| Sub-cohort name | Description | Estimated number of subjects |
|-------------------------------|--|--|
| HRV Immunogenicity sub-cohort | The serum anti-RV IgA antibody concentration and seropositivity 1 month after the second dose of the liquid HRV vaccine will be assessed in this sub-cohort of subjects. | 146 subjects (approximately half the number of subjects (73) from each study group)* |

* The first 73 subjects enrolled into each study group will be allocated to the sub-cohort.

- Recording of solicited local symptoms within 8 days follow-up period (Day 0 - Day 7) after the first dose of DPT-IPV vaccine.

- Recording of solicited general symptoms within 8 days follow-up period (Day 0 - Day 7) following administration of each dose of HRV vaccine and after the first dose of DPT-IPV vaccine.
- Recording of unsolicited symptoms within 31 days (Day 0- Day 30) following administration of each dose of HRV vaccine and after the first dose of DPT-IPV vaccine.
- Recording of causally related AEs from the first study vaccine up to Visit 7.
- Recording of SAEs from first study vaccine up to Visit 7.
- Recording of AEs/SAEs leading to withdrawal from the study from the first study vaccine.
- Recording of SAEs that are related to study participation (i.e. protocol-mandated procedures, invasive tests, a change from existing therapy) or are related to a concurrent GSK medication/vaccine from the time the subject consents to participate in the study until Visit 7.
- Type of study: self-contained.
- Data collection: Electronic Case Report Form (eCRF).

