4.2. Secondary endpoints

- Serum anti-RV IgA antibody concentration and seropositivity in a sub-cohort of subjects, 1 month after the second dose of the liquid HRV vaccine.
- Serum GMCs/GMTs for anti-diphtheria, anti-tetanus, anti-poliovirus serotypes 1, 2 and 3, anti-PT and anti-FHA antibodies, 1 month after the third dose of the DPT-IPV vaccine.
- Occurrence of solicited general symptoms during the 8-day (Days 0-7) follow-up period after each dose of liquid HRV vaccine.
- Occurrence of solicited local and general symptoms during the 8-day (Days 0-7) follow-up period after the first dose of DPT-IPV vaccine.
- Occurrence of unsolicited AEs during the 31-day (Days 0-30) follow-up period after each dose of the liquid HRV vaccine and the first dose of DPT-IPV vaccine, according to the Medical Dictionary for Regulatory Activities (MedDRA) classification.
- Occurrence of SAEs from the first dose of the study vaccine up to study end (Visit 7).

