| 2120 | Obvious incoherence, abnormal serology evolution or error in data (Eg; incoherence between CRF and results, wrong sample labelling) |

Table 4 Intervals between study visits for code 2080 and 2090

| Study Group | Interval | Optimal length of interval ¹ | Allowed interval ² |
|-------------------------|-------------------|---|-------------------------------|
| Co-administration group | Visit 1→Visit 2* | 30 days | 28 days - 42 days |
| | Visit 2→Visit 4 | 30 days | 28 days – 42 days |
| | Visit 4→Visit 6 | 56 days | 28 days - 56 days |
| | Visit 6→Visit 7 | 30 days | 21 days - 48 days |
| Staggered group | Visit 1→Visit 2* | 30 days | 28 days - 42 days |
| | Visit 2→Visit 3 | 15 days | 7 days - 21 days |
| | Visit 3→Visit 5** | 30 days | 28 days - 42 days |
| | Visit 5→Visit 6 | 45 days | 28 days – 56 days |
| | Visit 6→Visit 7 | 30 days | 21 days - 48 days |

¹. Whenever possible the investigator should arrange study visits within this interval.

². Subjects will not be eligible for inclusion in the According To Protocol (ATP) cohort for analysis of immunogenicity if they make the study visit outside this interval.

* Visit 2 should take place when the subject is 3 months of age or older.

**The period between Visit 2 and Visit 5 should be within 8 weeks.

There should be a time-period of at least 7 days between the administration of an inactivated vaccine and any other vaccine, and 28 days between the administration of a live virus vaccine and any other vaccine, in Japan. Please refer to the package inserts of *Rotarix* and *Squarekids* for more details.

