6. STATISTICAL ANALYSES

Note that standard data derivation rule and stat methods are described in Annex 1 and will not be repeated below.

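### The most-recent-dose rule halves the Days 0-30 safety window after DPT-IPV dose 1, in the Staggered group only

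*SAP*

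**What the plan says.** The secondary endpoint in SAP Section 4.2 concerns "unsolicited AEs during the 31-day (Days 0-30) follow-up period after each dose of the liquid HRV vaccine and the first dose of DPT-IPV". Section 2 plans data recording over the same period: "unsolicited symptoms within 31 days (Day 0- Day 30) following administration of each dose of HRV vaccine and after the first dose of DPT-IPV". Section 6.4.2 then requires that "separate analysis will be made for solicited symptom, unsolicited AE within 31 days post vaccination and concomitant medication", once for the two HRV doses and once for the first DPT-IPV dose.

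Annex 1 sets the derivation rules:

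- Section 11.2.1: "the onset day is the number of days between the last study vaccination & the onset/start date of the event".
- Section 11.2.2: "the relative dose for an event (AE, medication, vaccination) is the most recent study dose given before an event". Doses are numbered by vaccination visit, not by product, and an event on a vaccination day goes to that day's dose.

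Section 6 says of these rules that "standard data derivation rule and stat methods are described in Annex 1 and will not be repeated below", so they apply to every analysis unless something overrides them.

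The intervals are in Table 4 (Section 5.2.2). Staggered: "Visit 2→Visit 3 | 15 days | 7 days - 21 days". Co-administration: "Visit 2→Visit 4 | 30 days | 28 days – 42 days". Read with the schedules in Section 2, DPT-IPV dose 1 is given at Visit 2 in both groups. The next vaccination is HRV dose 2 at Visit 3 in the Staggered group and DPT-IPV dose 2 at Visit 4 in the Co-administration group.

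**The concern.** Any vaccination, of either product, closes the window of the dose before it. In the Staggered group HRV dose 2 arrives about halfway through the 31 days after DPT-IPV dose 1. An event 20 days after DPT-IPV dose 1, with Visit 3 on Day 15, gets onset day 5 and belongs to HRV dose 2. Under the written rules it cannot enter the DPT-IPV dose 1 result. In the Co-administration group nothing comparable happens until about Day 30.

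The denominators do not compensate. Section 11.2.5 keeps all vaccinated subjects and treats those without a reported event as event-free. The shorter window therefore lowers the Staggered percentage directly.

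At stake is a pre-specified secondary safety result that would not cover the period in its own title. The shortfall is tied to the randomised group, and it makes co-administration, the regimen under study, look worse.

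**Working it through.** **The plan's own figure.** Days 0 to 30 inclusive is 30 − 0 + 1 = 31 days, stated without distinction between groups.

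**Window kept under Annex 1.** If the next vaccination falls on Day k after DPT-IPV dose 1, events on Days 0 to k − 1 stay with that dose and an event on Day k moves to the next one. Days kept = min(31, k), with k from Table 4.

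| Group | Next vaccination, optimal (allowed) | Days kept, optimal | Days kept, allowed range |
|---|---|---|---|
| Staggered | Day 15 (7 to 21) | 15; 15/31 = 48.4% | 7 to 21; 22.6% to 67.7% |
| Co-administration | Day 30 (28 to 42) | 30; 30/31 = 96.8% | 28 to 31; 90.3% to 100% |

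The ranges do not overlap: at most 21 days against at least 28. The direction is the same at every allowed interval. Assigning each calendar day by the two rules, with visits at their optimal times, also gives 15 and 30 days.

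**What is not materially affected.**

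- After HRV dose 1 the next vaccination is 28 to 42 days later in both groups. The same holds after HRV dose 2 (Visit 2 to Visit 4 in Co-administration, Visit 3 to Visit 5 in Staggered). At optimal intervals each HRV window keeps 30 of 31 days in both groups.
- The Days 0-7 window loses a day only if Visit 3 falls on Day 7.
- Pooled per-subject summaries, and SAEs and related AEs up to Visit 7, do not depend on this dose assignment in any material way.

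**Illustration of size.** The SAP gives no AE incidence, so the true 31-day incidence p is assumed, equal in both groups, with visits at optimal intervals.

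- Constant hazard: shown incidence = 1 − (1 − p)^(k/31).
- Front-loaded (half the hazard in Days 0-7): shown incidence = 1 − (1 − p)^f, with f = 0.5 + 0.5 × (k − 8)/23 for k ≥ 8. So f(15) = 0.652 and f(30) = 0.978.

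| True p | Hazard | Staggered | Co-administration | Gap (points) |
|---|---|---|---|---|
| 5% | constant | 2.5% | 4.8% | 2.4 |
| 5% | front-loaded | 3.3% | 4.9% | 1.6 |
| 10% | constant | 5.0% | 9.7% | 4.7 |
| 10% | front-loaded | 6.6% | 9.8% | 3.2 |
| 20% | constant | 10.2% | 19.4% | 9.2 |
| 20% | front-loaded | 13.5% | 19.6% | 6.1 |
| 40% | constant | 21.9% | 39.0% | 17.1 |
| 40% | front-loaded | 28.3% | 39.3% | 11.0 |

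Gaps are taken before rounding.

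**Would the printed intervals differ?** Clopper-Pearson 95% limits with 146 per group, constant hazard:

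- p = 40%: 32/146 gives 15.5% to 29.5%; 57/146 gives 31.1% to 47.5%. These do not overlap.
- p = 20%: 15/146 gives 5.9% to 16.4%; 28/146 gives 13.1% to 26.5%. These overlap.

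Of the cases in the table, only the constant-hazard 40% case gives intervals that do not overlap.

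**A note on inputs.** The Section 10 group footnote prints the Staggered schedule differently from Section 2. Section 2 and Table 4 agree with each other and were used here; the footnote needs reconciling separately.

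**The case against.** The strongest reply is that Section 6.4.2 is study-specific and Annex 1 is standard text. Section 6.4.2 ties the separate analysis to the endpoint description, which is 31 days after the first DPT-IPV dose, and on that reading it already overrides Annex 1. But Section 6.4.2 states no onset rule, Section 6 makes Annex 1 the default, and no available sentence suspends it. A programmer following the document would truncate the window. Some mock tables and the table-of-contents file are not at hand, so an exception there cannot be ruled out.

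Other points stand in part:

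- **Limited harm.** Section 7 rules out comparative analyses beyond the confirmatory objectives, and Staggered events after Visit 3 still appear under HRV dose 2. Most rows are single preferred terms with low incidence, where the gap is a few points. The larger gaps belong to the row for any symptom. This bounds the severity but does not make the label correct.
- **Table 4 limits govern the ATP cohort, while safety uses the TVC.** Actual intervals may fall outside them, but a gap of about half a month follows from the Section 2 schedule itself (DPT-IPV at 3 months, HRV at 3.5).
- **Concomitant medication.** Its Days 0-30 window comes from Sections 6.4.1 and 6.4.2, not from the endpoint in Section 4.2. The truncation is the same, but the conflict with the stated endpoint concerns AEs.
- **Overlap after the fix.** In the Staggered group, Days 15-30 after DPT-IPV dose 1 would coincide with Days 0-15 after HRV dose 2. An event judged related because of HRV could then appear as related in the DPT-IPV table. Product and pooled tables may also differ slightly around Days 28-30. Both need a footnote. Shared events already occur in the Co-administration group, where the two vaccines are given at the same visit.
- **Alternatives exist.** A common shorter window or person-time would also restore symmetry, but neither delivers the 31-day result that Section 4.2 defines.

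**Conclusion.** The concern holds. As written, the SAP would report DPT-IPV dose 1 unsolicited AEs and concomitant medication as Days 0-30 while covering 15 days in the Staggered group and 30 in Co-administration at the optimal intervals (7 to 21 against 28 to 31 over the allowed ranges). The day counts follow directly from Annex 1, Table 4 and the visit schedule. The percentage gaps rest on assumed incidences, equal true rates and an assumed hazard shape.

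The fault is confined to one set of descriptive secondary safety results. The primary objective, the success criteria and the reporting of SAEs are untouched. It should be corrected before analysis, because the distortion follows the randomised group and nothing in the table would reveal it to a reader.

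**What to change.** Add one sentence to Section 6.4.2 or Annex 1: for the separate Days 0-30 analyses of unsolicited AEs and concomitant medication, onset day and window are derived from the date of the product dose concerned (HRV dose 1, HRV dose 2 or DPT-IPV dose 1), whatever other study vaccine is given in between. Both groups then have 31 days after DPT-IPV dose 1.

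Add a footnote to these tables saying that an event may appear under both products, that in the Staggered group the later part of the DPT-IPV dose 1 window overlaps the HRV dose 2 window (including for events judged related), and that product tables need not sum to the pooled tables. Keep the most-recent-dose rule for pooled and overall tables and for listings, so that no event is counted twice there.

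The cost is one sentence, one derivation and one footnote. No new AE data are needed, since Section 2 already plans recording of unsolicited symptoms for 31 days after DPT-IPV dose 1. Pooled counts do not change.
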